5 STUDY DESIGN

The SCOUT Study is a multi-center, centrally randomized, double-blind, placebo-controlled non-inferiority clinical trial. Children will be stratified based on the presence of fever at initial presentation of UTI symptoms and by specific antibiotic therapy prescribed by the original treating clinical provider. Children who have demonstrated clinical improvement five days after starting the originally prescribed antibiotic (afebrile and asymptomatic) will be randomized to standard arm or the short-course arm. Subjects enrolled prior to completion of Day 5 of their originally prescribed antibiotic treatment, will be instructed to complete Day 5 dosing prior to initiating SCOUT study product on Day 6. Subjects enrolled Day 6 should not have started the Day 6 of their originally prescribed antibiotic treatment. The SCOUT study product will consist of trimethoprim-sulfamethoxazole sulfamethoxazole (TMP-SMX), cefixime, cephalexin and the corresponding placebos. If a child initially prescribed cefdinir is enrolled, they will be randomized to either five additional days of cefixime or the cefixime placebo.

About 746 subjects will be enrolled in order to reach 672 evaluable subjects, but the total number that will be ‘enrolled / consented’ may exceed 746 if the study has not enrolled 672 evaluable for the primary endpoint.

Figure 1: Randomization

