Primary Analysis / Efficacy Analysis: The primary analysis will follow Intent-to-Treat (ITT) principles, with subjects analyzed according to randomized treatment assignment. In addition, a “per-protocol” analysis will be performed; the per-protocol analysis would include only subjects who were adherent to their assigned study regimen and completed 80% or more of the prescribed dose. All subjects taking at least one dose of study drug(s) who have been evaluated for treatment success at TOC visit or have failed treatment prior to TOC will be included in the ITT analysis (see the table below). The primary analysis will be a non-inferiority test comparing the number of symptomatic UTIs at the TOC visit between two treatment arms along with the 5% equivalence interval. The confidence interval of the difference in symptomatic UTI rates between the short-course and standard-of-care therapies will be calculated to evaluate whether this difference is less than or equal to the equivalence interval. This will be a one-sided test with $\alpha = 0.05$. Subjects with asymptomatic bacteriuria or who are asymptomatic with a

positive culture including pyuria will NOT be considered treatment failures for the primary outcome measure.

Table 9: SCOUT Study product Dosage Adherence

Antibiotic Drug	Antibiotic Dosage	80% of Expected Doses
Trimethoprim-Sulfamethoxazole (TMP-SMX)	8 mg/kg/day of Trimethoprim in 2 divided doses, Max 160mg BID Trimethoprim	Eight doses
Amoxicillin-Clavulanate*	45 mg/kg/day in 2 divided doses, Max 875 mg Q12H	Eight doses
Cefixime	8 mg/kg/day in 1 dose, Max 400 mg	Four doses
Cephalexin	50mg/kg/day in 3 divided doses	Twelve Doses

*Amoxicillin-clavulanate is no longer included as a study antibiotic, but subjects randomized to this treatment prior to its removal must have taken at least eight doses to be included in the per-protocol analysis.

Secondary Analysis:

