3.2 Sample size determination and power calculations

The primary aim of this study is to determine whether short-course antimicrobial therapy (five days) is non-inferior to standard-of care antimicrobial therapy (10

days) for the treatment of UTI in children with respect to reinfection of UTI through TOC visit Day 11-14. The treatment failure rate under the standard of care, R_0 , is expected to be 5%. This estimate is based on data from previously published studies [1, 2]. The power and sample size calculations are based on the assumption that recurrence under the short-course therapy, R_{SC} , will range from 5% to 9%.

In the non-inferiority test, on which power and sample size are based, the null hypothesis that short-course therapy is inferior to standard-of-care therapy is tested against the alternative that short-course therapy is non-inferior. That is, $H_0: R_{SC} > R_0 + \delta$ is tested against $H_a: R_{SC} \leq R_0 + \delta$, where δ is the “interval of equivalence,” the range in which the treatment failure rates of the two therapies would be considered clinically equivalent. We believe that an interval of equivalence of 5% would be clinically acceptable; a success rate of 95% for the standard-of-care therapy group when compared to 90% for the short-course therapy group. For all power and sample size calculations, the significance level (chance of incorrectly rejecting the null hypothesis) is $\alpha = 0.05$.

Table 1 gives the power for testing the non-inferiority hypothesis with a sample size of 300 evaluable subjects per arm and with equivalence intervals (i.e., δ) ranging from 2% to 5%. With 300 subjects per arm, there would be 87% power with $R_{SC} = 5\%$ and $\delta = 5\%$. The power decreases as either the equivalence interval decreases or as R_{SC} increases; in other words, as the recurrence rates of the two regimens become more similar, large sample sizes are required to discriminate between them.

Table 2 gives the sample sizes required to obtain 80% power with the same parameters for R_{SC} and δ . A sample size of 235 per arm is sufficient for 80% power with $R_{SC} = 5\%$ and $\delta = 5\%$, while larger sample sizes are required for larger values of R_{SC} or smaller values of δ . Finally, Table 3 gives the sample sizes required to obtain 90% power; a sample size of 326 subjects per arm would be required for 90% power with $R_{SC} = 5\%$ and $\delta = 5\%$.

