Table 1: Power (%) for comparing standard and shortened treatment for UTI

Interval of equivalence	Recurrence rate under shortened treatment				
	5%	6%	7%	8%	9%
2%	30	13	–	–	–
3%	51	28	12	–	–
4%	72	48	27	12	–
5%	87	69	46	25	12

Notes: Values for power in the table are given in percent and were calculated for comparing rates of recurrence between standard and shortened treatment for UTI, with sample sizes of 300 per arm and an assumed significance level of 0.05. The assumed recurrence rate for standard treatment is 5%. As an example, if the actual recurrence rate for shortened treatment is 6%, there is 28% power for finding non-inferiority with an equivalence interval of 3%. However, the power increases to 69% with an equivalence interval of 5%.

Table 2: Sample sizes for 80% power for non-inferiority of shortened vs. standard UTI antibiotic regimen

Interval of equivalence	Recurrence rate under shortened treatment				
	5%	6%	7%	8%	9%
2%	1,469	6,424	–	–	–
3%	653	1,606	6,962	–	–
4%	368	714	1,741	7,488	–
5%	235	402	774	1,872	8,001

This table gives sample sizes PER ARM for achieving 80% power for testing non-inferiority under the given values for recurrence rates and equivalence intervals. The significance level is assumed to be 0.05. The assumed recurrence rate for standard treatment is 5%. As an example, 653 study participants per arm (1,306 total) would be required for 80% power if the recurrence rate for the standard of care and shorted regimens were both 5%, with an equivalence interval of 3%.

Table 3: Sample sizes for 90% power for non-inferiority of shortened vs. standard UTI antibiotic regimen

Interval of equivalence	Recurrence rate under shortened treatment				
	5%	6%	7%	8%	9%
2%	2,034	8,898	–	–	–
3%	904	2,225	9,643	–	–
4%	509	989	2,411	10,371	–
5%	326	557	1,072	2,593	11,082

This table gives sample sizes PER ARM for achieving 90% power for testing non-inferiority under the given values for recurrence rates and equivalence intervals. The significance level is assumed to be 0.05. The assumed recurrence rate for standard treatment is 5%. As an example, 509 study participants per arm (1,018 total) would be required for 90% power if the recurrence rate for the standard of care and shortened regimens were both 5%, with an equivalence interval of 4%.

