4.1 Interim Analysis

After half of the subjects (373 subjects) have enrolled, an interim analysis for the primary endpoint of treatment failure rate will be performed. This efficacy analysis will test the null hypothesis that the treatment failure rate under short-course therapy is less than or equal to that of standard-of-care therapy; the alternative hypothesis is that the failure rate under short-course therapy is greater than using standard-of-care therapy. This test will be one-sided test of hypothesis of equal treatment failure rates between the short-course therapy and standard-of-care therapy with $\alpha=0.05$. We will calculate the difference in treatment failure rates between short-course therapy and standard-of-care therapy, and a one-sided 95% lower confidence limit using normal approximation for large samples. If the lower confidence limit exceeds zero, we will conclude that short-course therapy has a significantly higher failure rate than standard-of-care therapy. Since the interim analysis is for superiority of standard-of-care therapy and the final efficacy analysis is for non-inferiority of short-course therapy, there is no impact of the interim analysis on the Type I error of the final efficacy analysis and thus no adjustments to the significance level are required.

In addition, conditional power estimates may be calculated. The conditional power analysis is a re-assessment of the power given the results of the study to date. If the recurrence rate for short course therapy is smaller than expected relative to standard therapy, then there would be high conditional power; if the recurrence rate for short course therapy is greater than expected relative to standard therapy, then there would be lower power than initially expected. The need for this analysis will be

decided in conjunction with the DSMB, along with other data to be presented to the DSMB.

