4.2.2 Primary/Efficacy analysis

The primary endpoint of this study is the proportion of children experiencing treatment failure (symptomatic UTI) at the TOC visit (Day 11-14).

The primary analysis will follow intent-to-treat (ITT) principles, with subjects analyzed according to randomized treatment assignment (*Table 3 in Section 7.1*). In addition, a “per-protocol” analysis will be performed; the per-protocol analysis would include only subjects who were adherent to their assigned study regimen and completed more than 80% of the prescribed dose (*Table 4 in Section 7.1*). All subjects taking at least one dose of study treatment between Day 6 and Day 10 who have been evaluated for treatment success at TOC visit or have failed before TOC will be included in the ITT analysis (See Table 4 below).

The primary analysis will be a non-inferiority test comparing the proportion of children with symptomatic UTIs at the TOC visit between two treatment arms to evaluate whether the difference is within the 5% equivalence interval. This test will be conducted by calculating the one-sided 95% upper confidence limit for the difference in symptomatic UTI (treatment failure) rates between the short-course and standard-of-care therapies. If this limit is less than or equal to the equivalence interval (0.05), then we will conclude that short course therapy is not inferior to standard therapy. Subjects with asymptomatic bacteriuria or who are asymptomatic with a positive culture including pyuria will NOT be considered treatment failures for the primary outcome measure.

Table 4: SCOUT Study Medication Dosage Adherence

Antibiotic Drug	Antibiotic Dosage	80% of Expected Doses
Trimethoprim-Sulfamethoxazole (TMP-SMX)	8 mg/kg/day of Trimethoprim in 2 divided doses, Max 160mg BID Trimethoprim	Eight doses
Amoxicillin-Clavulanate	45 mg/kg/day in 2 divided doses, Max 875 mg Q12H	Eight doses
Cefixime	8 mg/kg/day in 1 dose, Max 400 mg	Four doses
Cephalexin	50mg/kg/day in 3 divided doses	Twelve Doses

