7.1 SAP Table shells

Table 1. Randomization review

	Arm 1: Standard Course Total= xxx N (%)	Arm 2: Short Course Total= xxx N (%)
Presence of fever		
Yes		
No		
Antibiotic Type		
TMP-SMX		
Amoxicillin-Clavulanate		
Cefixime		
Cefdinir		
Cephalexin		

Note: Chi-square tests for frequencies across two treatment groups

1. P=0.xxxx for Presence of fever versus No fever
2. P=0.xxxx for Antibiotic Type

Table 2. Demographic and baseline data

	Arm 1: Standard Course Total= xxx N (%)	Arm 2: Short Course Total= xxx N (%)	p-value
Age, Mean ± SD			
2 months -35 months			
3 – 6 years			
7 – 10 years			
Gender			
Male			
Female			
Race/ethnicity			
White			
Black/African American			
Asian			
Native Hawaiian/Other Pacific Islander			
American Indian/Alaska Native			
Multi-Racial			
Other			
Hispanic			
Yes			
No			

Table 2 Specifications

- Repeat the analysis on population 1 (ITT population) and 2 (per-protocol population) separately as Table 2a and 2b.
- Table 2 was designed to show the frequencies and column percentage of subjects within each category unless was specified as to show means and standard deviation. Some categorical variables may need to be created based on numeric values.

Table 3. Comparison of the proportion of subjects with symptomatic UTIs prior to or at the TOC visit for ITT population (Population 1) (Primary analysis)

	Arm 1: Standard Course Total= xxx N (%)	Arm 2: Short Course Total= xxx N (%)	Difference of proportion and one- sided 95% confidence limit
Treatment Failure			

SAS note: Using RISKDIFF ALPHA=0.10 in the TABLE STATEMENT of PROC FREQ procedures to calculate the difference of proportion and one sided 95% CI

Table 4. Comparison of the proportion of subjects with symptomatic UTIs prior to or at the TOC visit for per protocol population (Population 2) (Primary analysis)

	Arm 1: Standard Course Total= xxx N (%)	Arm 2: Short Course Total= xxx N (%)	Difference of proportion and one- sided 95% confidence limit
Treatment Failure			

Table 5. Comparison of the proportion of subjects with a recurrent infection at any time after the TOC visit for per protocol population (Population 3) (Secondary analysis, Endpoint a)

	Arm 1: Standard Course Total= xxx N (%)	Arm 2: Short Course Total= xxx N (%)	Difference of proportion and two- sided 95% confidence limit
Recurrent Infection			

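### The SAP does not state the interval method for the non-inferiority limit; the likely Wald reading gives an exact error of 5.4-5.5% against 5%, and a score-type limit would hold it

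*SAP*

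**What the plan says.** SAP 4.2.2 tests non-inferiority by "calculating the one-sided 95% upper confidence limit for the difference in symptomatic UTI (treatment failure) rates", short course against standard. The decision rule follows: "If this limit is less than or equal to the equivalence interval (0.05), then we will conclude that short course therapy is not inferior". Protocol 12.4 is no more specific: "The confidence interval of the difference in symptomatic UTI rates between the short-course and standard-of-care therapies will be calculated", as a one-sided test at alpha 0.05. Neither section says how the limit is computed.

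The SAS note under the Table 3 shell (SAP 7.1) reads: "Using RISKDIFF ALPHA=0.10 in the TABLE STATEMENT of PROC FREQ procedures to calculate the difference of proportion and one sided 95% CI". It gives the procedure, the option and the level, but no interval method. The Table 4 shell, the same comparison in the per-protocol population, has no note.

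For the interim look at the same endpoint, SAP 4.1 does name a method: "a one-sided 95% lower confidence limit using normal approximation for large samples".

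On size, SAP 3.2 says "a sample size of 326 subjects per arm would be required for 90% power" when both failure rates are 5% and the margin is 5 points. Protocol section 5 has a different target: "About 746 subjects will be enrolled in order to reach 672 evaluable subjects", or 336 per arm. Both sizes are used below.

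**The concern.** The less decisive limit, at the interim, has a stated method; the limit that decides the trial does not. With failures near 5% and a margin of 5 points, the arms have few events. In that setting the choice of interval method moves the upper limit by about 0.2 of a point, which can be enough to cross 0.05.

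The likely reading is also the less safe one. An uncorrected Wald limit sits slightly too low here, so non-inferiority would be declared a little more often than the stated 5% when short course is truly 5 points worse.

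**Working it through.** **Inputs.** Control failure rate 5%, margin 5 points and one-sided alpha 0.05 (SAP 3.2); 1:1 allocation (protocol summary); 326 per arm (SAP 3.2) and 336 per arm (protocol section 5, 672/2).

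**1. The plan's own figure.** The unpooled normal formula per arm is

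n = [R0(1−R0) + RSC(1−RSC)] × (1.645 + z_power)² / (δ − (RSC − R0))².

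With R0 = RSC = 0.05, δ = 0.05 and 90% power: (0.0475 + 0.0475) × (1.645 + 1.282)² / 0.05² = 325.4, rounded up to 326. This matches the SAP. The same formula, rounded up, reproduces all 28 entries of SAP 3.2 Tables 2 and 3. The sizing therefore uses the variance form that underlies a Wald limit, although this does not fix the analysis method.

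**2. Exact type I error.** For every pair of failure counts, work out whether the upper limit is at or below 0.05. Then add up the binomial probabilities of the passing pairs at the null boundary, where the short-course rate equals the control rate plus 0.05. The Wald limit is

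d + 1.645 × √[p1(1−p1)/n + p2(1−p2)/n].

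The score limit uses the variance at the maximum-likelihood rates restricted to a difference of 0.05.

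| Control rate | Wald, 326 | Wald, 336 | Score, 326 | Score, 336 |
|---|---|---|---|---|
| 2% (assumed) | 6.10% | 6.26% | 4.90% | 4.61% |
| 3% (assumed) | 5.80% | 5.94% | 4.88% | 4.79% |
| 4% (assumed) | 5.50% | 5.66% | 4.91% | 4.87% |
| **5% (plan)** | **5.39%** | **5.50%** | **4.90%** | **4.93%** |
| 6% (assumed) | 5.35% | 5.35% | 4.89% | 4.98% |
| 7% (assumed) | 5.26% | 5.25% | 4.92% | 4.98% |

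At the planned rate, Newcombe gives 5.05% (326) and 4.93% (336).

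**3. How often the verdict changes.** At 5% versus 10%, Wald and score disagree in 0.49% (326) and 0.57% (336) of trials. With up to 60 failures per arm, every disagreement is Wald passing and score failing.

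Example: 17 short-course and 9 standard failures out of 326 each. The difference is 8/326 = 2.454 points and the standard error is 1.530 points, so the Wald limit is 2.454 + 1.645 × 1.530 = 4.97 (non-inferior). The score limit is 5.16 (not shown). At 336 per arm the limits are 4.82 and 5.01. With 14 versus 5 failures, Wald and score give 4.92 and 5.18 (326), and 4.78 and 5.03 (336).

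**4. Power at 5%/5%.**

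| Per arm | Wald | Score | Newcombe |
|---|---|---|---|
| 326 | 89.9% | 88.5% | 88.5% |
| 336 | 90.9% | 89.2% | 89.3% |

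The loss from Wald to score is 1.4 points at 326 and 1.7 points at 336.

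**The case against.** The strongest reply is that the gap is narrow. The SAP names the procedure, option, level, direction and cut-off. The interim wording and the sizing formula point the same way, so one explicit phrase naming the Wald limit would close the gap and match the sizing. This stands in part: it would remove the ambiguity, but it would leave the small excess error, which a score-type limit removes.

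A second reply is that the harm is about 0.4-0.5 of a point on a nominal 5%. The larger figures need control failure of 2-3%, whereas the documents give only 5%; the 17 versus 9 example has a standard-arm rate of 2.7%. This stands and limits the weight of the point.

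A third is that the enumeration ignores the stratified randomisation. If strata differ in risk, the unstratified Wald variance is too large and the error falls. In an illustrative simulation with two equal strata and 326 per arm, assumed control rates of 3%/7% gave about 5.3%, and 1%/9% about 5.2%. This trims the excess but does not remove it.

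Two stronger inferences are not supported. A reader might infer that the plan leaves open anything from a continuity-corrected limit (error 4.0%) to an uncorrected one (5.5%); no section mentions a continuity correction. A reader might also infer that the plan has committed to a Wald limit with inflated error. The SAP never says so for the final analysis, and what the SAS option does without a method keyword is not in the documents.

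**Conclusion.** The omission is real, and it concerns the limit that decides the trial. The Wald reading is an inference from three consistent signs: the bare software note, the interim wording and the sizing formula. On that reading the exact one-sided error at the planned boundary is 5.4% (326 per arm) or 5.5% (336), against the stated 5%. A score limit brings it to about 4.9%.

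The calculation assumes independent binomial arms of equal size, no difference in risk between strata, and no effect of the interim look. The excess grows if control failure is below 5% and shrinks if it is above. The point is worth acting on because the correction is cheap; the design itself is sound on this matter. Miettinen-Nurminen is not essential: Newcombe performs about as well.

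**What to change.** State in SAP 4.2.2 and in the Table 3 SAS note, and add the same note to Table 4, wording such as: *The primary limit is the Miettinen-Nurminen score one-sided 95% upper limit for the risk difference, short course minus standard, taken as the upper end of the two-sided 90% interval. The uncorrected Wald limit is reported as a sensitivity analysis.* A Newcombe limit may be named instead.

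Restate power at 5%/5% in SAP 3.2 as about 88.5% (326 per arm) or 89.2% (336 per arm). The change should be made before unblinding.

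The cost is one software option, a sentence or two of text, and 1.4-1.7 points of power relative to Wald, which puts power just under the planned 90%. No extra enrolment is proposed.

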differences in microbial carriage and composition between and within subjects over time, we will calculate the UniFrac distance [PMID: 20827291] between all pairs of samples. UniFrac is a measure of the fraction of the evolutionary tree relating all observed taxa that is not overlapping between two samples. To visualize these within- and between-subject differences (beta diversity) and to obtain principal components for subsequent statistical testing, we will perform dimensionality reduction using principal coordinates analysis. To enable tests for shifts in the relative abundance of both broad and specific bacterial taxa with respect to the host factors mentioned above, we will collapse the reference-based OTUs according to taxonomy at the genus and phylum levels using QIIME. This will produce culture-independent fractional observation counts of bacterial taxa in all samples.

We will test for overall differences in microbiome composition between short-course and standard-course antibiotics. To test for associations between individual bacterial taxa and these groups, we will perform non-parametric Mann-Whitney U tests. We will perform a similar test for association of microbiome biodiversity with treatment and between-sample diversity as well as gammaproteobacteria relative abundance.. In all cases the significance of association will be determined after correcting for multiple comparisons using false discovery rate.

Subpopulation Analyses: Treatment effects for the primary and secondary outcome measures will be estimated as differences between proportions and compared for subpopulations defined by age groups, febrile or non-febrile UTI (at original UTI diagnosis), and type of originally prescribed antibiotic. First, proportions will be tabulated as two-sample comparisons and chi-square tests for treatment differences in the outcomes within subgroups will be calculated. Factors where significant differences are observed will be further assessed using logistic regression analysis, assuming that the logistic model fits the data. Goodness of fit test will be reported for model checking. Treatment-by-subpopulation interactions will be tested using likelihood ratio tests. The power of these comparisons is expected to be low for both primary and secondary endpoints. The study is only likely to detect marked differences in treatment effects in these subpopulations.

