4.2.5 Sub-population analyses

Treatment effects for the primary and secondary endpoints will be estimated as differences between proportions and compared for subpopulations defined by age (defined initially as less than 3 years old, 3 to 6 years old, and 7 to 10 years old), febrile or non-febrile UTI, type of originally prescribed antibiotic, and site. First, proportions will be tabulated as two-sample comparisons and chi-square tests for treatment differences in the endpoints within subgroups will be calculated (*Table 12-*

17 in Section 7.1). Factors where significant differences are observed will be further assessed using logistic regression analysis (*Table 18-23 in Section 7.1*). Goodness of fit test will be reported for model checking. Treatment-by-subpopulation interactions will be tested using likelihood ratio tests. The power of these comparisons is expected to be low for both primary and secondary endpoints. The study is only likely to detect marked differences in treatment effects in these subpopulations. These analyses will use only the per-protocol population with appropriate exclusions (see Section 5.1). Because these analyses are exploratory, significance level at 0.05 will be used.

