5.1 Tables

▪ Definition of populations

- **Population 1:** All subjects taking at least one dose of study treatment between Day 6 and Day 10 who have been evaluated for treatment success at TOC or have failed prior to TOC (ITT population)
- **Population 2:** The enrolled subjects who were adherent to their assigned study regimen and completed more than 80% of the prescribed dose between Day 6 and Day 10 (per-protocol population)
- **Population 3:** Subjects in population 2 who did not experience a treatment failure.
- **Population 4:** Subjects in population 2 who have a stool sample at TOC visit. Some treatment failures will not have a sample collected at TOC because they failed prior to TOC. Treatment failures without the sample at TOC would be excluded from population 4.

▪ Definition for a subject having primary endpoint

The primary endpoint of this study is the proportion of children experiencing treatment failure (symptomatic UTI) at the TOC visit (Day 11-14).

▪ Data handling

- Treat blanks and “.” as missing unless specified otherwise.

6. References

1. [name] R, Chan E. A meta-analysis of randomized, controlled trials comparing short- and long-course antibiotic therapy for urinary tract infections in children. *Pediatrics*. May 2002; 109(5):E70-70.

7. Appendices

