Antibiotic Type TMP-SMX Amoxicillin-Clavulanate Cefixime Cefdinir Cephalexin			
Site CHOP PITT			

Table 15. Comparison of the proportion of subjects with clinical symptoms that may be related to a UTI prior to or at the TOC visit for subpopulation (Population 2) (Secondary endpoint d)

	Arm 1: Standard Course Total= xxx N (%)	Arm 2: Short Course Total= xxx N (%)	p-value for Chi-square test
Age Group 2 month – 35 months 3 – 6 years 7-10 years			
Febrile Febrile UTI Non-Febrile UTI			
Antibiotic Type TMP-SMX Amoxicillin-Clavulanate Cefixime Cefdinir Cephalexin			
Site CHOP PITT			

Table 16. Comparison of the proportion of subjects with positive urine cultures prior to or at the TOC visit for subpopulation (Population 2) (Secondary endpoint e)

	Arm 1: Standard Course Total= xxx N (%)	Arm 2: Short Course Total= xxx N (%)	p-value for Chi-square test
Age Group 2 month – 35 months 3 – 6 years 7-10 years			
Febrile Febrile UTI Non-Febrile UTI			
Antibiotic Type TMP-SMX Amoxicillin-Clavulanate Cefixime Cefdinir Cephalexin			
Site CHOP PITT			

Table 17. Comparison of Risk of emergent colonization with antimicrobial resistant E. coli or K. pneumoniae in Gastrointestinal Tract for Subpopulations (Population 4) (Secondary endpoint c)

	Arm 1: Standard Course Total= xxx N (%)		Arm 2: Short Course Total= xxx N (%)		p- value 1	p- value 2
	TOC visit	Outcome visit	TOC visit	Outcome visit		
Age Group						
2 – 35 months						
3 – 6 years						
7-10 years						
Febrile						
Febrile UTI						
Non-Febrile UTI						
Antibiotic Type						
TMP-SMX						
Amoxicillin- Clavulanate						
Cefixime						
Cefdinir						
Cephalexin						
Site						
CHOP						
PITT						

p-value 1 and p-value 2 will reported from Chi-square test comparing the proportions between sub-populations and treatment arms at TOC visit, and Outcome assessment visit, respectively.

Table 18. Multivariable Logistic Regression Analysis for Treatment failure (Symptomatic UTI at TOC visit) (Population 1) (Primary endpoint)

	Odds ratio	95% CI	p -value
Arm 1 Standard Course(reference)			
Arm 2 Short Course			
Covariates			

Interaction Term			

CI: Confidence Interval

SAS tips: SCALE=NONE in the MODEL statement of the PROC LOGISTIC procedure to generate deviance and Pearson chi-square for goodness of fit test.

Table 19. Multivariable Logistic Regression Analysis for Recurrent Infection at any time after the TOC visit (Population 3) (Secondary endpoint a)

	Odds ratio	95% CI	p -value

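### The SAP Table 17 footnote describes a chi-square across subgroups and arms together, which conflicts with the within-subgroup arm tests of SAP 4.2.5 and, read literally, does not isolate treatment length

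*SAP*

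**What the plan says.** The body of the SAP (4.2.5, Sub-population analyses) sets the method for the subgroup tables, citing Tables 12 to 17: "chi-square tests for treatment differences in the endpoints within subgroups will be calculated". Protocol 12.4 has the same rule: "chi-square tests for treatment differences in the outcomes within subgroups will be calculated". The next step in SAP 4.2.5 depends on the result: "Factors where significant differences are observed will be further assessed using logistic regression analysis". Effect modification has its own test: "Treatment-by-subpopulation interactions will be tested using likelihood ratio tests". No multiplicity adjustment is made: "Because these analyses are exploratory, significance level at 0.05 will be used".

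Tables 12 to 16 in SAP 7.1 have one chi-square p-value column and no further specification. Table 17 covers emergent resistant colonization (secondary endpoint c), has two visits and two p-value columns, and carries its own note: "p-value 1 and p-value 2 will reported from Chi-square test comparing the proportions between sub-populations and treatment arms at TOC visit". The note goes on to assign the second p-value to the Outcome Assessment visit. It gives no table dimensions or degrees of freedom, and does not say whether there is one p-value per subgroup row or one per factor.

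Table 17 uses Population 4: "Subjects in population 2 who have a stool sample at TOC visit". Its factors are age ("defined initially as less than 3 years old, 3 to 6 years old, and 7 to 10 years old"), fever at original diagnosis, originally prescribed antibiotic (five rows) and site.

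**The concern.** The footnote and 4.2.5 describe different tests for the same table. A test of the treatment difference within a subgroup asks whether short and standard course differ among, say, children under 3 years. A test across subpopulations and arms asks whether any of the subgroup-by-arm cells differ, so it responds to differences between subgroups as well as between arms.

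A programmer working from the shell could reasonably code the second. The p-value would then sit beside a comparison of arms but could be small because resistance emerges more often with one antibiotic or in one age group, whatever the length of treatment. Since 4.2.5 sends factors with significant differences on to logistic regression, a factor could reach that step for the wrong reason. The endpoint deserves care: limiting resistance is the trial's rationale, and SAP 4.2.3 states a directional hypothesis in favour of the short course.

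**Working it through.** **Plan's own figure.** The documents give no figure for Table 17. The sample size only sets the scale. SAP 3.2: n per arm = (1.645 + 1.282)² × 2 × 0.05 × 0.95 / 0.05² = 325.4, so 326 per arm and 652 in total, as stated. Population 4 is a subset of the per-protocol set, so it should be smaller. I assume 540, and use 400 and 652 as a range.

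**What a joint test contains.** With K = 3 subgroups and two arms there are 6 cells and 2K − 1 = 5 degrees of freedom: 2 for subgroup, 1 for arm and 2 for their interaction. The 5% critical value is 11.07. The within-row test of 4.2.5 has 1 degree of freedom, for arm only.

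**Rejection with no arm effect.** Under the joint reading the statistic is approximately noncentral chi-square on 5 degrees of freedom, with

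λ = Σ n_cell (p_cell − p̄)² / [p̄(1 − p̄)], n_cell = 540/6 = 90.

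Example, true rates 20/15/10% in both arms: p̄ = 0.15, λ = 90 × 4 × 0.05² / (0.15 × 0.85) = 7.06, and P(reject) is about 50%.

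The rates below are assumptions. Simulated figures are for 540 children, 1:1 allocation and equal subgroups.

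| True rates, same in both arms | λ | Joint test, approximation | Joint test, simulated | 4.2.5 test, per row |
|---|---|---|---|---|
| 15/15/15% | 0 | 5% | 5% | about 5% |
| 16/15/14% | 0.28 | 6% | 6% | about 5% |
| 18/15/12% | 2.54 | 19% | 19% | about 5% |
| 20/15/10% | 7.06 | 50% | 51% | about 5% |
| 25/15/10% | 15.1 | 87% | 86% | about 5% |

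The result moves with the population size. At 18/15/12% the joint test rejects in 14% of trials with 400 children and 22% with 652; at 20/15/10%, 38% and 59%. For five equal antibiotic groups at 10/10/15/20/20% and 652 children it rejects in 57%.

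**Screening step.** If a factor goes forward when any of its rows is significant (4.2.5 does not say), the within-row tests send a three-level factor forward in 1 − 0.95³ = 14% of trials with no arm effect, whatever the spread between subgroups. For the joint test the figure is 6% to 86% over the unequal-rate rows above. The joint test is thus the worse screen only once the spread is moderate.

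**The case against.** The strongest reply is that the joint test is only one reading. The phrase may be shorthand for arm comparisons by subpopulation, and the note may exist mainly because Table 17 alone has two visits and must say which p-value belongs to which. SAP 4.2.5 names Table 17 in its range, and protocol 12.4 agrees with it. This stands in part: the documents do not establish that a joint test was intended. The two texts still differ, and the shell is what would be programmed.

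The assumed spreads are also not in the documents. For antibiotic there is only the sub-study hypothesis (protocol 5.1) that the agent as well as the length of therapy affects flora and resistance; for age there is nothing. The endpoint counts change since enrollment, so differences already present at enrollment are not events in themselves. This stands, and is why the size is given as a range.

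A reader might go further and infer that these p-values will be significant whenever resistance differs by subgroup. They will not: at 16/15/14% the joint test rejects in 6% of trials.

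A reader might also infer that real effects of treatment length would be missed. The documents do not support that. Table 10 compares the arms overall at both visits, SAP 4.2.3 adds longitudinal models, and Table 23 has separate lines for arm, covariates and interaction. Nor do the within-row tests win on power. With a true 15% against 8% in every subgroup and 540 children, each row has about 31% power and the joint test about 46%. The case for 4.2.5 is that its p-value answers the stated question, not that it is more powerful.

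**Conclusion.** The inconsistency is real and is in the current SAP text. Read literally, the Table 17 footnote gives a p-value that does not isolate treatment length: with no arm effect it rejects in about 6% to 86% of trials over the unequal-rate scenarios tabulated, against about 5% per row for the test in 4.2.5. These figures assume the joint reading, 540 children in Population 4, equal subgroups and resistance rates that the documents do not supply.

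The consequence is modest. The analysis is labelled exploratory, no primary conclusion rests on Table 17, and the overall arm and interaction questions are answered elsewhere. A prognostic factor that enters the logistic model for the wrong reason does not by itself create a false arm effect. This is a wording correction worth making before the tables are programmed.

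**What to change.** Replace the Table 17 footnote with wording such as: p-value 1 and p-value 2 are from chi-square tests comparing short course with standard course within each subgroup row, at the TOC visit and the Outcome Assessment visit respectively (Section 4.2.5). Add one p-value per factor and visit from the likelihood ratio interaction test that 4.2.5 already plans. It would also help to state in 4.2.5 whether one significant row is enough to send a factor to the logistic step, given the 14% chance shown above for three rows.

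The cost is one footnote, one added column or line, and the matching program statement. It needs no patients, no new data and no new method.
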